Official Title: A Randomized, Multicenter, Double-Blind, Placebo-Controlled, Phase III Clinical Study to Evaluate the Efficacy and Safety of Intrathecally Administered RO7234292 (RG6042) in Patients With Manifest Huntington's Disease

NCT Number: NCT03761849

Document Dates: SAP Version 3: 12-May-2022

SAP Version 1: 16-December-2019

STATISTICAL ANALYSIS PLAN

TITLE: A RANDOMIZED, MULTICENTER, DOUBLE-BLIND, PLACEBO-CONTROLLED, PHASE III CLINICAL STUDY TO EVALUATE THE EFFICACY AND SAFETY OF INTRATHECALLY ADMINISTERED RO7234292 (RG6042) IN PATIENTS WITH MANIFEST HUNTINGTON'S DISEASE

PROTOCOL NUMBER: BN40423 Version 4 and onwards

STUDY DRUG: RO7234292 (Tominersen)

VERSION NUMBER: 3

IND NUMBER: 137873

EUDRACT NUMBER: 2018-002987-14

SPONSOR: F. Hoffmann-La Roche Ltd

PLAN PREPARED BY: [REDACTED], Ph.D.
[REDACTED], M.Sc.
[REDACTED], M.Sc.

DATE FINAL: Version 1: 16 December 2019
Version 2: 1 April 2022

DATE AMENDED: See electronic date stamp on the last page of this document.

STATISTICAL ANALYSIS PLAN AMENDMENT APPROVAL

CONFIDENTIAL

This is an F. Hoffmann-La Roche Ltd document that contains confidential information. Nothing herein is to be disclosed without written consent from F. Hoffmann-La Roche Ltd.

STATISTICAL ANALYSIS PLAN AMENDMENT RATIONALE

The Statistical Analysis Plan (SAP) for Study BN40423 has been amended in accordance with the Protocol BN40423 Version 4 and onwards.

Study BN40423 was originally designed (under Protocol Versions 1-3) to include three dosing regimens under a double-blinded monthly dosing paradigm: RO7234292 every 4 weeks (Q4W), RO7234292 every 8 weeks (Q8W) (with alternating placebo), and placebo Q4W. The Sponsor decided to stop enrollment under this original protocol containing this blinded monthly dosing paradigm and revised the protocol with a major protocol amendment in March 2019 to include three dosing regimens under a double-blinded bi-monthly dosing paradigm: RO7234292 Q8W, RO7234292 every 16 weeks (Q16W) arm (with alternating placebo), and placebo Q8W.

The details of this amendment including the rationale are in Protocol Version 4.

In March 2021, following the recommendation from the independent Data Monitoring Committee (iDMC) as a consequence of a regular iDMC safety review, the Sponsor issued an Urgent Safety Measure (USM) to permanently halt the dosing in the BN40423 study and implemented a new protocol amendment (Protocol Version 6).

Amendments made in the SAP from Version 1 to 2 includes following changes: Details on the study design were updated to reflect the study design as per Protocol Version 4 and onwards. Outcome measures were updated to consider outcome measures as per Protocol Version 6 and it was clarified that efficacy and biomarker outcome measures will be evaluated based on change from baseline at Week 69 due to Sponsor's decisions to discontinue study treatment as of 22 March 2021. Efficacy outcome measures (primary, secondary, and exploratory) and exploratory health status utility outcome measures were added and the order in which the different outcome measures are listed were adjusted for consistency with Protocol Version 6. Additionally, biomarker outcome measures were specified in accordance with Protocol Version 6.

Key changes made to the SAP from Version 2 to Version 3 are summarized below:

- Definition of baseline was updated in Sections 4.4, 4.9, 4.9.3, and 4.9.6.

Additional minor changes have been made to improve clarity and consistency.

TABLE OF CONTENTS

STATISTICAL ANALYSIS PLAN AMENDMENT RATIONALE.....	2
1. BACKGROUND	6
2. STUDY DESIGN	7
2.1 Protocol Synopsis.....	8
2.2 Endpoints.....	8
2.2.1 Primary Efficacy Endpoint.....	8
2.2.2 Secondary Efficacy Endpoints.....	8
2.2.3 Exploratory Efficacy Endpoints	9
2.2.4 Safety Endpoints	9
2.2.5 Pharmacokinetic Endpoints	10
2.2.6 Immunogenicity Endpoints.....	10
2.2.7 Biomarker Endpoints	10
2.2.7.1 Primary Biomarker Endpoint.....	10
2.2.7.2 Secondary Biomarker Endpoints	10
2.2.7.3 Exploratory Biomarker Endpoints	10
2.2.8 Exploratory Health Status Utility Endpoints	10
2.3 Determination of Sample Size	11
2.4 Analysis Timing	13
3. STUDY CONDUCT	13
3.1 Randomization.....	13
3.2 Data Monitoring	13
4. STATISTICAL METHODS	13
4.1 Analysis Populations	13
4.1.1 Intent-to-Treat Population.....	13
4.1.2 Safety Population	14
4.1.3 PK Population.....	14
4.2 Analysis of Study Conduct.....	14
4.3 Analysis of Treatment Group Comparability	14
4.4 Efficacy Analysis.....	14
4.4.1 Covariate Adjustment	15
4.4.2 Primary Efficacy Endpoint.....	15

4.4.3	Secondary Efficacy Endpoints	16
4.4.4	Exploratory Efficacy Endpoints	16
4.4.5	Subgroup Analyses	17
4.4.6	Post-Hoc Exploratory Analysis	17
4.5	Pharmacokinetic Analyses.....	18
4.6	Immunogenicity Analyses.....	19
4.7	Biomarker Analyses.....	20
4.8	Exploratory Health Status Utility Analyses.....	20
4.9	Safety Analyses	21
4.9.1	Exposure of Study Medication	21
4.9.2	Adverse Events	21
4.9.3	Laboratory Data.....	22
4.9.4	Vital Signs and ECG.....	23
4.9.5	Columbia-Suicide Severity Rating Scale	23
4.9.6	Montreal Cognitive Assessment	23
4.9.7	Safety MRI.....	24
5.	ANALYSIS OF OFF-TREATMENT FOLLOW-UP DATA.....	24
5.1	Mixed Model Repeated Measurements	24
5.2	Slope Analysis	24
5.3	Other Analyses of Off-Treatment Follow-up Data.....	25
6.	REFERENCES	26

LIST OF TABLES

Table 1	CSF Safety Laboratory Normal Ranges.....	23
---------	--	----

LIST OF FIGURES

Figure 1	Visit Schedule Scenarios for Early Treatment Termination (Applicable to All Patients from 22 March 2021)	7
----------	---	---

LIST OF APPENDICES

Appendix 1	Reporting Windows by Endpoints.....	27
------------	-------------------------------------	----

1. **BACKGROUND**

Study BN40423 is a Phase III, randomized, placebo-controlled, double-blind, multicenter clinical study to evaluate the efficacy, safety, pharmacokinetic (PK), and biomarker effects of intrathecally (IT) administered RO7234292 in patients with manifest Huntington's disease (HD).

Study BN40423 was originally designed (under Protocol Versions 1-3) to include three dosing regimens under a double-blinded monthly dosing paradigm: RO7234292 every 4 weeks (Q4W), RO7234292 every 8 weeks (Q8W) (with alternating placebo), and placebo Q4W. The Sponsor decided to stop enrollment under this original protocol containing this blinded monthly dosing paradigm and revised the protocol with a major protocol amendment in March 2019 to include three dosing regimens under a double-blinded bi-monthly dosing paradigm: RO7234292 Q8W, RO7234292 every 16 weeks (Q16W) arm (with alternating placebo), and placebo Q8W.

The details of this amendment including the rationale are in Protocol Version 4.

Prior to stopping the enrollment in Protocol Versions 1-3 on 29 March 2019, 108 patients were randomized, referred to as the "Original Design Cohort" (ODC). The ODC will not be included in the primary efficacy and safety analysis of the new study design (Protocol Version 4 and onwards). The Sponsor made this decision to prevent the potential bias that would have been introduced to the trial results if patients under different regimens (monthly and bi-monthly) were contained in the same analysis. Instead, ODC patients have been discontinued from Study BN40423 and offered enrollment into the long-term open-label extension study (BN40955).

Analysis for the Protocol Versions 1-3 (ODC) are described in Statistical Analysis Plan (SAP) Version 1.

In March 2021, following the recommendation from the independent Data Monitoring Committee (iDMC) as a consequence of a regular iDMC safety review, the Sponsor issued an Urgent Safety Measure (USM) to permanently halt the dosing in the BN40423 study and implemented a new protocol amendment (Protocol Version 6). This allowed patients to enter the off-treatment follow-up period, to monitor their safety and efficacy endpoints after the treatment discontinuation. At the same time, the Sponsor has been unblinded, to allow the start of exploratory analyses as soon as possible, for internal decision making on further clinical development of RO7234292.

This SAP will describe the statistical analysis of the efficacy and safety analyses of the cohort enrolled under Protocol Version 4 and onwards. The statistical analysis will be performed on the data collected up to the treatment termination (referred as "on-treatment period" thereafter) and data collected after the treatment termination (referred as "off-treatment follow-up period" thereafter).

2. STUDY DESIGN

[figure not shown]
Approximately 801 patients will be enrolled in Study BN40423 under Protocol Version 4 and onwards. Prospective patients will undergo screening assessments during a 4-week screening period.

Upon completion of the screening period, eligible patients will be randomized in a 1:1:1 ratio to receive 120 mg RO7234292 Q8W, 120 mg RO7234292 Q16W, or placebo Q8W by IT injection. To maintain the study blind and integrity, patients in the 120 mg RO7234292 Q16W arm will also receive placebo every 8 weeks (i.e., alternating doses of active drug and placebo every 8 weeks).

Following the iDMC recommendation and Sponsor's decision to discontinue study treatment in this study, as of 22 March 2021, all patients will transition to the Early Treatment Termination (ETT) schedule within 56 days after treatment discontinuation as shown in [Figure 1](#).

The language used in this SAP supersedes that in the protocol and protocol synopsis.

Figure 1 Visit Schedule Scenarios for Early Treatment Termination (Applicable to All Patients from 22 March 2021)

EoT=end of treatment; ETT=early treatment termination; FU=follow-up.

^a The ETT visit should be performed within 56 days of the decision to discontinue study treatment. A telephone safety follow-up call will be conducted every 8 weeks between the clinic visits, to check for any change in patient status since the patient's last visit.

2.1 PROTOCOL SYNOPSIS

Please refer to Protocol Version 6 for the protocol synopsis. For additional details, see the Schedule of Assessments in Protocol Version 6, Appendix 1a and the Schedule of Assessments for Early Treatment Termination in Protocol Version 6, Appendix 1b.

2.2 ENDPOINTS

Following the iDMC recommendation and Sponsor's decision to discontinue study treatment in this study, as of 22 March 2021, only data collected up to 22 March 2021 will be used to evaluate the efficacy of RO7234292. By that date, approximately 80% of the participants reached their Week 69 visit, therefore the efficacy and biomarker outcome measures will be evaluated based on change from baseline at Week 69 (rather than change from baseline at Week 101).

However, all outcome measures are listed below as planned per protocol (i.e., referring to change from baseline at Week 101).

2.2.1 Primary Efficacy Endpoint

- Change from baseline in the composite Unified Huntington's Disease Rating Scale (cUHDRS) score at Week 101

Note: The primary efficacy endpoint for the U.S. Food and Drug Administration (FDA) will be change from baseline in the Total Functional Capacity (TFC) score at Week 101.

Due to the iDMC recommendation as explained in Section 2.2 change from baseline at Week 69 (rather than change from baseline at Week 101) will be analyzed for endpoint listed above.

2.2.2 Secondary Efficacy Endpoints

- Change from baseline in scores for the following individual scales at Week 101:
 - TFC
 - Total Motor Score (TMS)
 - Symbol Digit Modalities Test (SDMT)
 - Stroop Word Reading (SWR) Test

Note: For the U.S. FDA, the first secondary endpoint will be change from baseline in the cUHDRS score at Week 101 instead of TFC, as TFC will be the primary endpoint.

- Change from baseline in the Clinical Global Impression, Severity Scale (CGI-S) score at Week 101
- Proportion of patients with a decrease from baseline of at least 1 point on the TFC at Week 101
- Proportion of patients with a decline from baseline of at least 1.2 points on the cUHDRS at Week 101

- Proportion of patients with an unchanged or improved score on the Clinical Global Impression, Change Scale (CGI-C) score from baseline at Week 101

Due to the iDMC recommendation as explained in Section 2.2, change from baseline at Week 69 (rather than change from baseline at Week 101) will be analyzed for all endpoints listed above.

2.2.3 Exploratory Efficacy Endpoints

- Change from baseline in the Apathy Evaluation Scale (AES) score at Week 101
- Change from baseline in the Symptoms of Major Depressive Disorder Scale (SMDDS) score at Week 101
- Change from baseline in the Huntington's Disease Daily Activities Scale (HD-DAS) score at Week 93
- Change from baseline in the Patient Global Impression, Severity Scale (PGI-S) score at Week 101
- Change from baseline in the Quality of Life in Neurological Disorders (Neuro-QoL) Cognition Function Short Form at Week 101
- Change from baseline in the Huntington's Disease Speaking Difficulty Item Scale (HD-SDI) score at Week 101
- Change from baseline in the Huntington's Disease Companion-Reported Irritability and Angry Outbursts Scale (HD-CIAOS) score at Week 101
- Change from baseline in the in-clinic patient-reported EuroQoL 5-Dimension Questionnaire (5-level version; EQ-5D-5L) index-score and visual analogue scale (VAS) at Week 101
- Change from baseline in the sensor-based measures collected by the Roche HD mobile application (app; smartphone and wrist-worn wearable) at Week 101

Due to the iDMC recommendation as explained in Section 2.2, change from baseline at Week 69 (rather than change from baseline at Week 101) will be analyzed for all endpoints listed above.

2.2.4 Safety Endpoints

- Incidence and severity of adverse events (AEs), with severity determined according to the Adverse Event Severity Grading Scale
- Change from baseline in Montreal Cognitive Assessment (MoCA)
- Change from baseline in vital signs
- Change from baseline in ECG parameters
- Change from baseline in clinical laboratory results
- Proportion of patients with suicidal ideation or behavior, as assessed by Columbia-Suicide Severity Rating Scale (C-SSRS) score at each visit, including

detailed focus on any individual cases identified as having severe ideation or behavior during the study conduct

2.2.5 Pharmacokinetic Endpoints

- Concentration of RO7234292 in plasma at specified timepoints
- Trough concentration of RO7234292 in cerebrospinal fluid (CSF) at specified timepoints

The exploratory pharmacokinetic/pharmacodynamic (PK/PD) outcome measures are:

- Relationship between plasma profiles and/or trough CSF concentrations and/or PK parameters for RO7234292 and efficacy endpoints
- Relationship between plasma profiles and/or trough CSF concentrations and/or PK parameters for RO7234292 and safety endpoints

2.2.6 Immunogenicity Endpoints

- Incidence of anti-drug antibodies (ADAs) at specified timepoints relative to the prevalence of ADAs at baseline
- Titer and antibody subtype, determined if ADAs are identified

The exploratory immunogenicity outcome measure is:

- Relationship between ADA status and efficacy, safety, or PK endpoints

2.2.7 Biomarker Endpoints

2.2.7.1 Primary Biomarker Endpoint

- Change from baseline in CSF mutant huntingtin (mHTT) protein level at Week 101

2.2.7.2 Secondary Biomarker Endpoints

- Change from baseline in whole and regional brain volumes (caudate, whole brain, and ventricular), as determined by structural magnetic resonance imaging (MRI), at Week 101
- Change from baseline in CSF neurofilament light chain (NfL) protein level at Week 101

2.2.7.3 Exploratory Biomarker Endpoints

- Relationship between biomarkers in blood, plasma, and CSF and efficacy, safety, PK, immunogenicity, or other biomarker endpoints
- Relationship between imaging biomarkers (e.g., putamen, cortical grey matter, cortical white matter volumes, resting state functional MRI signal) and efficacy, safety, PK, immunogenicity, or other biomarker endpoints

2.2.8 Exploratory Health Status Utility Endpoints

- Change from baseline in patient- and companion-reported EQ-5D-5L Index and VAS scores at specified timepoints

- Change from baseline in companion self-reported and proxy-reported Health Utilities Index Mark 2 (HUI2) and Health Utilities Mark 3 (HUI3) scores at specified timepoints
- Change from baseline in patient- and companion-reported Work Productivity and Activity Impairment (WPAI) scores at specified timepoints

2.3 DETERMINATION OF SAMPLE SIZE

The planned sample size is adequate to capture meaningful clinical decline on both the TFC and cUHDRS and was estimated applying a meta-analysis on data available from non-interventional studies (TRACK-HD, COHORT, ENROLL-HD) and a randomized placebo-controlled study (2CARE). Results of the meta-analysis on the change from baseline at 24 months in TFC suggested a natural decline of 1.36 points and a corresponding pooled standard deviation of 1.78. A conservative treatment discontinuation rate at Week 101 for patients receiving placebo or active is assumed to be 20% and 15% respectively.

Using these assumptions, 267 patients per arm was estimated to provide approximately 80% power, at a two-sided ≤ 0.025 level, to detect a 40% slowing of clinical decline for RO7234292 as compared with placebo at 101 weeks. The proposed sample size was estimated based on simulations (further described below). The assumed treatment effect translates into an expected average decline of ~ 0.82 points at 101 weeks for the RO7234292 arms. The minimal detectable difference with these assumptions is ~ 0.38 points.

Given the above sample size, the cUHDRS, the more sensitive outcome measure, is powered at 80%, at a two-sided ≤ 0.025 level, to detect a 30% slowing of clinical decline for RO7234292 as compared with placebo at 101 weeks. Since there are presently no therapies available to stop or slow clinical progression in HD, any slowing of clinical progression of overall functional decline or linked overall functional, cognitive, and motor decline may be considered meaningful, such that between a 20%-40% slowing of decline, translating to approximately 2.5-4.5 months per year of time saved from progression, would represent a meaningful treatment effect.

Description of simulations to derive the sample size

The design used for the simulation was simplified to consider only 2 treatment arms (placebo and active) and 2 post-baseline time-points (Week 49 and Week 101).

1. The following algorithm was run and repeated 500000 times:
Generate change from baseline values in TFC at Week 49 and Week 101 for **N active patients** according to the following bivariate normal distribution:

$$\begin{pmatrix} y_{wk49} \\ y_{wk101} \end{pmatrix} = N\left(\mu = \begin{pmatrix} 0.47 \\ 0.82 \end{pmatrix}, \Sigma = \begin{pmatrix} 1.56^2 & 1.8 \\ 1.8 & 1.78^2 \end{pmatrix}\right)$$

where $y_{_wk49}$ and $y_{_wk101}$ is the change from baseline in TFC respectively at Week 49 and Week 101, μ is the assumed true change at those two timepoints and Σ is the variance-covariance matrix. The assumed covariance of 1.8 corresponds to a correlation coefficient of 0.65. Subsequently:

- set to missing, due to any treatment and/or disease progression related reasons (TDPR), both values at Week 49 and Week 101 for 5% of the N active patients. Set to missing, due to non-treatment or disease progression related reasons (NTDPR), both values at Week 49 and Week 101 for additional 2.5% of the N active patients.
 - set to missing, due TDPR, only the value at Week 101 for additional 5% of the N active patients. Set to missing, due to NTDPR, only the value at Week 101 for additional 2.5% of the N active patients.
2. Generate change from baseline values in TFC at Week 49 and Week 101 for N **placebo patients** according to the following bivariate normal distribution:

$$\begin{pmatrix} y_{_wk49} \\ y_{_wk101} \end{pmatrix} = N\left(\mu = \begin{pmatrix} 0.79 \\ 1.36 \end{pmatrix}, \Sigma = \begin{pmatrix} 1.56^2 & 1.8 \\ 1.8 & 1.78^2 \end{pmatrix}\right)$$

where $y_{_wk49}$ and $y_{_wk101}$ is the change from baseline in TFC respectively at Week 49 and Week 101, μ is the assumed true change at those two timepoints and Σ is the variance-covariance matrix. Subsequently:

- set to missing both values at Week 49 and Week 101 for 10% of the N placebo patients
- set to missing only the value at Week 101 for additional 10% of the N placebo patients

Given how missing data will be imputed, it is not relevant to differentiate missing data into TDPR versus NTPDR for placebo patients.

3. Apply multiple imputation and derive 20 complete datasets. Missing data on placebo patients were imputed from the placebo arm. Missing data on active patients, depending if due to TDPR or NTDPR reasons, were imputed respectively from the active or the placebo arm.
4. Use a t-test to compare active versus placebo at Week 101 for each completed dataset and pool the result ([Rubin 1987](#)) to derive an estimate of the treatment effect, including a p-value.

Across the 500000 simulations, the power achieved, with the N patients per arm was calculated, by dividing the number of times the two-sided p-value (in Step 4) was below 2.5% by 500000. The above procedure was repeated by only changing the N until the calculated power was close to 80%.

2.4 ANALYSIS TIMING

The final analysis will be conducted once all patients have either reached Week 101 or withdrawn early from the study and data have been cleaned and verified and the database has been locked.

Following the iDMC recommendation and Sponsor's decision to discontinue study treatment in this study, as of 22 March 2021, the main statistical analysis will be performed on the data collected up to 22 March 2021. The data collected after 22 March 2021 will be analyzed in an exploratory off-treatment follow-up analysis.

3. STUDY CONDUCT

3.1 RANDOMIZATION

Approximately 801 patients are planned to be randomized to receive placebo, RO7234292 Q8W 120 mg or RO7234292 Q16W 120 mg in a 1:1:1 ratio using permuted block randomization. An independent Interactive Voice or Web Response System (IxRS) provider will conduct randomization and hold the treatment assignment code. No stratification is applied in this study.

3.2 DATA MONITORING

An iDMC will be employed to monitor and evaluate cumulative patient safety throughout the study. It is anticipated those safety reviews will occur approximately every 4 months (further details are provided in a separate iDMC charter).

Following the iDMC recommendation to halt the dosing in Study BN40423, the scope of the iDMC has been revised and it is now focusing on a comparison of the on-treatment period (data collected up to treatment termination) against the off-treatment follow-up period (data collected after treatment termination). Further details are provided in the updated iDMC charter.

4. STATISTICAL METHODS

4.1 ANALYSIS POPULATIONS

4.1.1 Intent-to-Treat Population

The intent-to-treat (ITT) population will consist of all randomized patients who received any study treatment. Randomized patients who receive therapy different from the one assigned at randomization will be summarized in the group according to their planned randomized treatment.

The ITT population will be the primary population for all analyses of primary and secondary efficacy variables.

4.1.2 Safety Population

The ITT population will also be used for all analyses of safety data.

For the purpose of all safety analyses, at the time of unblinding, it will be assessed whether at any time during the course of the study, patients received a treatment different from the one they were randomized to.

For patients who were randomized to placebo but received any active treatment by error, if there is any safety signal of concern present, they will be summarized under the active treatment group; otherwise will be summarized under placebo.

The safety data during such switching period will be provided separately.

The final decision on this will only be possible after unblinding.

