4.6 IMMUNOGENICITY ANALYSES

For the analysis, the following definitions based on Shankar et al. (2014) as well as a Sponsor's definition for ADA with neutralizing potential, will be used to describe patients' RO7234292 immunogenicity as follows:

- **ADA Negative**
 - ADA negative all samples: Patients who have no pre-existing ADA (i.e., antibodies reactive with the drug that are present in patients before treatment) or are missing ADA data before drug administration and who have all negative ADA results following drug administration, and treatment unaffected ADA-negative patients.
 - Treatment unaffected ADA: Subset of ADA negative patients who have pre-existing ADA but do not have a ≥ 4 fold increase in ADA titer following drug administration compared to baseline measurement.
- **ADA Positive**
 - Treatment induced: ADA developed de novo (seroconversion) following drug administration. Patients who have no pre-existing ADA or are missing ADA data before drug administration and who have at least one ADA positive sample following drug administration.
 - Treatment boosted: Patients who have pre-existing ADA and have a ≥ 4 fold increase in ADA titer following drug administration compared to baseline measurement.
- **Transient ADA**
 - Treatment-induced ADA detected only at one sampling time point during the on-treatment or off-treatment follow-up period (excluding the last sampling time point).
- **Persistent ADA**
 - Treatment-induced ADA detected at 2 or more sampling time points during the on-treatment or off-treatment follow-up period; or detected on last sampling time point.
- **ADA with Neutralizing Potential**
 - An ADA positive patient with declining or increasing PK based on visual assessment, and corroborated by PD markers.

Immunogenicity will be analyzed in patients included in the safety population who had at least one ADA assessment. Patients will be grouped according to treatment received or, if no treatment is received prior to study discontinuation, according to treatment assigned. The numbers and proportions of ADA-positive patients and ADA-negative patients at baseline (baseline prevalence) will be summarized by treatment group. For those who are ADA-positive, titers will be estimated as well as antibody subtype. In addition, the numbers and proportions of ADA-positive patients and ADA-negative

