3.1.2 Safety Population

The ITT population will also be used for all analyses of safety data.

For the purpose of all safety analyses, at the time of unblinding, it will be assessed whether at any time during the course of the study, patients received a treatment different from the one they were randomized to.

For patients who were randomized to placebo but received any active treatment by error, if there is any safety signal of concern present, they will be summarized under the active treatment group; otherwise will be summarized under placebo.

The final decision on this will only be possible after unblinding.

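### Placebo patients given active drug in error are moved to the active safety group only if an undefined safety signal is present, so the outcome decides the group

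*SAP*

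**What the plan says.** SAP Version 3, Section 4.1.2, starts from the intent-to-treat set: "The ITT population will also be used for all analyses of safety data". Under Section 4.1.1, patients in that set who receive a different therapy from the one assigned "will be summarized in the group according to their planned randomized treatment".

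Section 4.1.2 then makes an exception, which begins "For patients who were randomized to placebo but received any active treatment by error" and continues: "if there is any safety signal of concern present, they will be summarized under the active treatment group; otherwise will be summarized under placebo". It adds "The safety data during such switching period will be provided separately" and "The final decision on this will only be possible after unblinding".

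SAP Version 1, Section 3.1.2, written for the Original Design Cohort, has the same condition ("if there is any safety signal of concern present, they will be summarized under the active treatment group") but no sentence on a separate display.

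Within the same safety population, Section 4.6 uses another rule for immunogenicity: "Patients will be grouped according to treatment received or, if no treatment is received prior to study discontinuation, according to treatment assigned". That rule does not depend on outcome.

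**The concern.** A safety table compares how often events occur in groups defined by exposure or by assignment. Here, for mis-dosed placebo patients, the safety result helps to choose the group in which that result is counted. The exposure is the same whether or not a signal appears, and only the outcome differs. Patients with a signal carry their events to active. Patients without one do not join the active denominator and remain in the placebo denominator.

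The rule also cannot be applied reproducibly as written:

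- It does not say what counts as a signal of concern or who judges it.
- It does not require the signal to follow the erroneous dose.
- It sends the patient to the active group, although there are two active arms (Q8W and Q16W).
- It gives no safety grouping of its own for mix-ups between the active arms, or for active patients given placebo.

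A mis-dosed placebo patient without a signal would be placebo in the adverse event tables but could be active in the immunogenicity tables. Section 4.9.2 asks for adverse events by antibody status, which needs one consistent grouping.

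At stake is whether the main safety rates in each arm estimate what they appear to estimate.

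**Working it through.** The SAP gives no figure on this point, so there is none to reproduce. The check asks what the rule does when the drug has no effect.

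**Inputs**
- n = 267 per arm (SAP Section 2.3), comparing placebo with one active arm that receives every reassigned patient.
- p = true event risk, the same for everyone. Assumed; 10% in the main illustration, 5% to 50% in the range.
- k = number of placebo patients mis-dosed. Not given; 1 to 20 tried.
- The rule is read per patient, and the signal is taken to be the event being tabulated. Expected counts are used throughout.

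**Rates under the SAP rule.** On average kp mis-dosed patients have the event and move:
- active = (np + kp)/(n + kp)
- placebo = (np − kp)/(n − kp)

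**Rates under a rule that ignores outcome**
- All k moved: active = (np + kp)/(n + k) = p; placebo = (np − kp)/(n − k) = p. Difference 0.
- None moved: both rates are np/n = p. Difference 0.

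**Results at p = 10% (np = 26.7)**

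| k | Active, SAP rule | Placebo, SAP rule | Spurious excess | Risk ratio |
|---|---|---|---|---|
| 1 | 26.8/267.1 = 10.03% | 26.6/266.9 = 9.97% | +0.07 points | 1.007 |
| 5 | 27.2/267.5 = 10.17% | 26.2/266.5 = 9.83% | +0.34 points | 1.034 |
| 20 | 28.7/269 = 10.67% | 24.7/265 = 9.32% | +1.35 points | 1.145 |

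Over p = 5% to 50% and k = 1 to 20, the excess runs from +0.04 to +3.75 points, always against active.

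**Where the bias comes from.** Take k = 20. Grouping by treatment received gives 28.7/287 = 10.0% on active and 24.7/247 = 10.0% on placebo. The numerators equal those under the SAP rule. The only difference is the 20 − 2 = 18 event-free mis-dosed patients, whom the SAP rule leaves in the placebo denominator. Moving the patients with events is not itself the error; failing to move the others with them is.

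**The case against.** Much can be said for the plan.

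- **The effect is small and the count may be zero.** This stands. One mis-dosed patient at 10% risk shifts the comparison by about 0.07 points, and the larger figures need numbers of errors that the documents do not report.
- **The direction is conservative.** This stands. The bias runs against active drug, so it does not hide harm. The safety outputs are descriptive summaries and listings, and efficacy grouping is untouched. The tables still misstate both rates.
- **Reassignment is visible.** Switching-period data are shown separately, and Section 4.2 has major protocol deviations listed and evaluated. That helps a careful reader but leaves the main tables as they are.
- **The trigger may be narrow.** A signal of concern need not mean any adverse event. If it is narrower, fewer patients move and the bias falls mainly on the triggering events. If it means a signal in the data as a whole, the arithmetic above does not apply directly, but grouping still depends on safety results. Either way the term needs a definition or removal.

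Two stronger readings are tempting, and the documents do not support them.

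First, a reader might take a rare event with 3 cases in each arm of 267, move one mis-dosed placebo case, and report (4/268)/(2/266) = 1.99. That does not show the defect, because grouping by treatment received moves the same patient and gives the same ratio. It also assumes that the mis-dosed patient has the event, which at that risk happens with probability 3/267, about 1.1%. In expectation the ratio is (3.0112/267.0112)/(2.9888/266.9888), about 1.007.

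Second, a reader might infer that the unblinded decision, in a trial halted after a safety review, taints the rule. Finding mis-dosed patients needs the treatment codes under any as-treated rule. The same condition already stood in SAP Version 1, dated 16 December 2019, before the March 2021 halt.

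**Conclusion.** The point holds. Section 4.1.2 lets the safety result decide the analysis group of a mis-dosed placebo patient. Following the rule as written produces, on average, an excess on active when there is no drug effect, whereas a rule that ignores outcome produces none.

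The sizes calculated rest on 267 patients per arm, an assumed event risk, an assumed number of mis-dosed patients, a per-patient reading, and a signal that coincides with the tabulated event. The defect in the rule does not depend on the assumed risk or count; its size does.

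Because the bias is small in expectation, runs against active drug and affects descriptive tables, this is a should-fix matter. It does not show that the trial's safety conclusions are wrong.

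**What to change.** In Section 4.1.2:

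1. Delete the condition on a safety signal and use one rule that ignores outcome for all safety tables. Treatment received is the natural choice, because Section 4.6 already uses it.
2. State which active arm, Q8W or Q16W, receives a placebo patient given active drug in error.
3. State how mix-ups between Q8W and Q16W, and active patients given placebo, are grouped.
4. State how time and events before the first erroneous active dose are counted.
5. Keep the separate switching-period display and add an as-randomized table as a sensitivity analysis.

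SAP Version 1, Section 3.1.2, carries the same condition, so safety tables for the Original Design Cohort should be read with the same caution.

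The cost is one paragraph of SAP text and a little more tabulation. No new data are needed. The sponsor has been unblinded since March 2021, so the new rule cannot be presented as set before unblinding. Its protection is that it does not depend on outcome.
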